6.4.2. Secondary Efficacy Analyses

6.4.2.1. Definition of Secondary Endpoint

The following treatment outcome definitions will be used for the assessment of efficacy relative to baseline: Clinical Outcome.

- Clinical Cure: Complete resolution of signs and symptoms with total composite score of 0 on the VSS Scale and with no additional antifungal therapy required based on investigator's judgment.
- Clinical Improvement: Partial resolution of signs and symptoms with total composite score of 1 or 2 on the VSS Scale and with no additional antifungal therapy required based on investigator's judgement.
- Clinical Success: At least 50% reduction from Baseline in the total composite VSS score with no additional antifungal therapy required based on investigator's judgment .
- Clinical Failure: Persistence and/or worsening of signs and symptoms or need for additional antifungal therapy (this definition also applies to cycle 2 patients).

The following mycological outcome definitions will be used for the assessment of subjects with mycological response.

- Mycological Eradication: Negative culture for growth of *Candida* species .
- Presumed Eradication: Subject is asymptomatic, therefore cultures not done .
- Mycological Persistence: Positive culture for growth of *Candida* species.

6.4.2.2. Main Analysis Approach

Frequency and percentage of subjects with total composite score equal or less than 2 on the VSS scale at the TOC and FU visits, and total composite score equal or less than 1 on the VSS scale at the TOC and FU visits will be summarized.

Frequency and percentage of subjects with clinical improvement, clinical success, mycological response, with both clinical cure and mycological response at TOC and FU visit, with clinical cure at FU visit will be summarized.

The value and absolute change in total composite VSS score from baseline to the TOC and FU visits will be summarized with descriptive statistics.

6.4.3. Exploratory Efficacy Analyses

6.4.3.1. Definition of Exploratory Endpoints

The Quality-of-Life Questionnaire (QOL) used was developed by SCYNEXIS to measure the absolute change from Baseline in 6 VVC symptoms. Each symptom was measured on a 10-point visual analog scale (0 being None and 10 being Extreme) from patient recall over the preceding week. In addition, two questions were included on Patient Global Impression of Change (PGIC) to measure changes in overall health and overall sexual satisfaction since study start. Ratings were on a scale of 1 (Very much improved) to 7 (Very much worse).

Time to resolution of symptom is defined as the time from initiation of study treatment until resolution of the symptom, which is measured by VSS score = 0. The data will be collected from initiation of study treatment to last FU visit in Cycle 1 and Cycle 2 separately. Time to resolution of any symptom and time to resolution of all symptoms will be summarized by treatment for subjects in MITT, ITT and PP population.

6.4.3.2. Main Analysis Approach

The value and absolute change in QOL score from baseline to the TOC and FU visits will be summarized with descriptive statistics for each symptom by visit. The value and absolute change of mean score of QOL questions (excluding PGIC) from baseline to the TOC and FU visits will be summarized with descriptive statistics by visit. Proportion and 95% CI of each category will be summarized using Clopper-Pearson method for 2 PGIC questions by visit.

Time to resolution of signs and symptoms after initiation of study drug will be analyzed using Kaplan-Meier methods. Median survival time at which half of the subjects had reached resolution of symptoms and its 95% CI will be reported using Brookmeyer-Crowley method. Pairwise treatment comparisons of subjects in group B 3 days vs. subjects in group B 7 days will be performed using log-rank test.

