14.8. Rating of Vulvovaginal Symptoms by the Subject Using the VSS Scale

Subjects will be asked to rate their vulvovaginal symptoms at Screening, Baseline (Day 1), during telephone interviews on Days 3, 5 and 7, at the TOC visit and at the FU visits.

Subjects will also assess their symptoms at unscheduled visits, as needed.

If the subject experiences persistence or worsening or recurrence of symptoms that per the investigator's assessment (e.g. symptoms ≥ 4) warrant the use of rescue antifungal therapy, the rating of the symptoms that led to the use of rescue antifungal therapy must be documented in the eCRF and a vaginal examination with rating of signs by the investigator should be completed. If the investigator's rating of the vulvovaginal signs and vaginal samples collection are not possible prior to the initiation of the rescue therapy, they should still be completed as soon as possible after rescue therapy is initiated.

Subjects will rate their symptoms of infection using the VSS Scale, where each vulvovaginal symptom will be given a numerical rating based on severity, as follows:

- Itching: absent = 0; mild = 1; moderate = 2; severe = 3
- Burning: absent = 0; mild = 1; moderate = 2; severe = 3
- Irritation: absent = 0; mild = 1; moderate = 2; severe = 3

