14.11. Rating of Vulvovaginal Signs by the Investigator Using the VSS Scale

The investigator (or qualified designee) will perform vulvovaginal examinations to rate the subject's signs of infection at the Screening, TOC and first FU visits at 14 days after EOT. The vulvovaginal examination will be repeated at the rest of the FU visits only if the subject presents with symptoms. Otherwise, no additional vulvovaginal examination will be conducted, or signs rated. Vulvovaginal examinations may be conducted at unscheduled visits, if needed.

If the subject experiences persistence or worsening or recurrence of symptoms that per the investigator's assessment (e.g. symptoms ≥ 4) warrant the use of rescue antifungal therapy, the subject may be enrolled into Treatment Cycle 2 and receive additional treatment with ibrexafungerp for a period up to 14 days as recommended by the investigator and following discussion with the sponsor.

Whether or not a subject enters Treatment Cycle 2, or be prescribed rescue therapy, a vaginal examination with rating of signs by the investigator should be completed prior to initiation of rescue therapy. If the investigator's rating of the vulvovaginal signs is not possible prior to the initiation of the rescue therapy, it should still be completed as soon as possible after rescue therapy is initiated.

Investigators will assess the signs of infection using the VSS Scale provided in Section 21 [Appendix 2]), a standardized, predefined scale where each sign of the vagina and/or vulva will be given a numerical rating based on severity, as follows:

- Edema: absent = 0; mild = 1; moderate = 2; severe = 3
- Erythema: absent = 0; mild = 1; moderate = 2; severe = 3
- Excoriation or fissures: absent = 0; mild = 1; moderate = 2; severe = 3

Other findings will be recorded using the most relevant medical term in the abbreviated physical examination page of the eCRF.

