4.2.2. Secondary Endpoints

Efficacy as measured by:

- The percentage of subjects with clinical improvement:
 - Total composite score of 2 on the VSS scale at the TOC and FU visits
 - Total composite score of 1 on the VSS scale at the TOC and FU visits.
- The percentage of subjects with total composite score equal or less than 2 and equal or less than 1 on the VSS scale at the TOC and FU visits.
- The percentage of subjects with clinical success (at least 50% reduction from baseline in the total composite VSS score) with no additional antifungal therapy required based on investigator's judgment) at the TOC and FU visits.
- The percentage of subjects with mycological response (defined as a negative culture for growth of *Candida spp.* or subject is asymptomatic, therefore culture not done) at the TOC and FU visits.
- The percentage of subjects with both clinical cure and mycological response at the TOC and FU visits.
- The percentage of subjects with clinical cure at the FU visits.
- The absolute change in total composite VSS score from baseline to the TOC and FU visits.

Exploratory Endpoints:

- Absolute improvement in QOL outcomes at TOC and FU visits compared to baseline as measured by QOL survey.
- Subjects whose signs and symptoms have resolved enough that additional antifungal treatment was not required based on clinical judgement.
- Time to resolution of symptoms.

Safety and Tolerability as measured by:

Adverse events (AEs), vital signs, treatment discontinuation, and safety laboratory tests.

5. Study Design

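### Time to resolution is defined on symptoms but analysed on signs and symptoms, and the SAP gives no censoring rule for Cycle 2 entry or other antifungal use

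*SAP*

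**What the plan says.** The exploratory endpoint is listed in SAP 4.2.2 as "Time to resolution of symptoms". SAP 6.4.3.1 keeps to that: "Time to resolution of symptom is defined as the time from initiation of study treatment until resolution of the symptom", measured by a VSS score of 0. It names two variants: "Time to resolution of any symptom and time to resolution of all symptoms will be summarized by treatment".

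The analysis section, SAP 6.4.3.2, widens the event: "Time to resolution of signs and symptoms after initiation of study drug will be analyzed using Kaplan-Meier methods". Its next sentence narrows it again, to "Median survival time at which half of the subjects had reached resolution of symptoms and its 95% CI". The same paragraph plans a log-rank test of 3 days against 7 days in Group B.

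On data cut-off, SAP 6.4.3.1 says: "The data will be collected from initiation of study treatment to last FU visit in Cycle 1 and Cycle 2 separately". The SAP gives no censoring rule for this endpoint. SAP 6.1.2 says only that missing data are not imputed unless otherwise specified.

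The two kinds of rating follow different schedules. Under Protocol 14.8, after Baseline, subjects rate symptoms "during telephone interviews on Days 3, 5 and 7, at the TOC visit and at the FU visits". Under Protocol 14.11, the investigator rates "signs of infection at the Screening, TOC and first FU visits at 14 days after EOT". At later follow-up visits signs are rated only if symptoms are present, and examinations at unscheduled visits are allowed.

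**The concern.** Two programmers could build different event variables from the same SAP. One would take events from the phone contacts onward. The other would wait for a sign rating, and so could not see early resolution, which is when treatment durations of one, three and seven days might be expected to differ.

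The second issue is who leaves the Cycle 1 risk set, and why. SAP 6.5 opens Cycle 2 to subjects with insufficient improvement and to responders who recur. Protocol 11.4 ends visits for a subject given other antifungal therapy and classes her as terminated for lack of efficacy. Kaplan-Meier treats a censored subject as having the same future chance of resolution as those still followed. That is doubtful for someone who left because she had not responded. What is at stake is the resolution curve, sometimes its median, and the comparison of the two randomised Group B arms.

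**Working it through.** The documents give no expected median, event count or power for this endpoint, so there is no planned figure to reproduce. The schedule comes from the documents. All rates below are assumptions, with 50 subjects per arm as in SAP 6.3.6.

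**Step 1. Earliest recordable event.**

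| Event | Scheduled ratings after Baseline | Earliest |
|---|---|---|
| Symptoms | Phone Days 3, 5, 7 (± 1); TOC; all FU visits | about Day 2 (3 − 1) |
| Signs and symptoms | TOC (14 ± 3 days after Baseline); EOT+14; later only if symptomatic | about Day 11 (14 − 3) |

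After EOT+14 an asymptomatic subject has no scheduled sign rating. A later sign-inclusive resolution may therefore never be confirmed.

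**Step 2. Effect on the median.** Exponential true times were simulated (1,500 runs per setting), with events recorded at the next nominal rating visit. Kaplan-Meier medians for the 7-day arm:

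| True median (days) | Symptom schedule | Signs required (Day 14, EOT+14) |
|---|---|---|
| 4 | 5 | 14 |
| 7 | 7 | 14 |
| 10 | 14 | 14 |

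**Step 3. Why censoring is the default.** Under Protocol section 15, Cycle 2 restarts the visit schedule at Baseline. SAP 6.1.1 recalculates baselines for Cycle 2, and SAP 6.5.1 gives Cycle 2 its own exploratory analysis. A Cycle 2 entrant's later ratings therefore belong to Cycle 2. With no other rule, Kaplan-Meier on Cycle 1 data censors her at her last Cycle 1 rating.

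**Step 4. Size of the censoring effect.** Let n = 50, r = resolved by TOC, c = unresolved subjects entering Cycle 2 at TOC, m = n − r − c, and e = later resolutions among the m.

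- Censored at entry: 1 − (1 − r/n)(1 − e/m)
- Kept as not resolved: (r + e)/n

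The grid covered resolution by TOC of 30, 40 and 50%; Cycle 2 entry among the unresolved of 20, 40 and 60%; and later resolution among the rest of 20 and 40%. That is 18 scenarios, with counts rounded to whole subjects.

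- Smallest gap (50%, 20%, 20%): r = 25, c = 5, m = 20, e = 4. Censored: 1 − 0.50 × 0.80 = 60%. Kept: 29/50 = 58%. Gap 2 points.
- Largest gap (30%, 60%, 40%): r = 15, c = 21, m = 14, e = 6. Censored: 1 − 0.70 × 8/14 = 60%. Kept: 21/50 = 42%. Gap 18 points.

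**Step 5. Effect on the median.** If half or more have resolved by TOC, the curve has reached 50% before anyone is censored and the median does not move. In 4 of the 18 scenarios the median is reached only because of censoring: 56.7% vs 46%, 60% vs 42%, 53.3% vs 48%, and 50% vs 44%. In all four, 30 or 40% had resolved by TOC.

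**Step 6. Effect on the arm comparison.** Take two arms, each with 40% resolved by TOC and about 40% later resolution among the rest, differing only in Cycle 2 entry.

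- 20% entry: r = 20, c = 6, m = 24, e = 10. Censored: 1 − 0.60 × 14/24 = 65%. Kept: 30/50 = 60%.
- 60% entry: r = 20, c = 18, m = 12, e = 5. Censored: 1 − 0.60 × 7/12 = 65%. Kept: 25/50 = 50%.

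A 10-point difference on the kept basis disappears under censoring. The log-rank statistic itself was not computed for this example.

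**The case against.** The phrase in 6.4.3.2 is probably loose drafting. The endpoint name, the definition, both variants and the next sentence all say symptoms, and on that reading the phone ratings count. This is a fair account of the likely intent. But 6.4.3.2 is the section a programmer works from, and VSS is a scale of both signs and symptoms, so a score of 0 does not settle the matter.

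A reader might infer that signs can never be seen before TOC. The documents do not support that. Protocol 14.11 allows unscheduled examinations, and Protocol 11.4 asks for a sign rating when other antifungal therapy is warranted. What stands is that no sign rating is scheduled between Screening and TOC.

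A reader might also infer that the SAP drops non-responders at Cycle 2 entry. It does not say so. Its text on taking data to the last follow-up visit is compatible with keeping them as non-events. What stands is that no rule is stated and that the software default would be informative.

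Nor does every Cycle 2 entrant matter. A subject whose symptoms resolved and then recurred has already had her event. The same is true, on the symptom definition, of one who enters on signs alone with symptoms at 0.

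Finally, the planned outputs are a median and a log-rank test, not a final percentage, and counting Cycle 2 entrants as not resolved is a choice of estimand rather than the one true value. Both points are right, and they limit the size of the concern.

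**Conclusion.** The point holds in two parts of unequal certainty. The mismatch between definition and analysis is plain on the text. Followed literally, 6.4.3.2 moves the first scheduled event to about Day 11 and leaves the phone ratings unused. The missing rule for Cycle 2 entry and non-study antifungals is also plain. That it would lead to informative censoring is an inference from the split by cycle and the Kaplan-Meier default.

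If unresolved subjects were censored there, cumulative resolution would be higher by roughly 2 to 18 percentage points on the assumed rates, since the documents supply none. The direction is upward whenever some of those remaining resolve later. The median changes only when fewer than half have resolved before the censoring. The 3-day versus 7-day comparison is affected if Cycle 2 entry differs by arm.

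The endpoint is exploratory, the study is not powered for comparisons, and the primary endpoint is untouched. The correction is still worth making before database lock, because it decides which data enter the analysis.

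**What to change.** In SAP 6.4.3.2, replace *resolution of signs and symptoms* with *resolution of any symptom and resolution of all symptoms, as defined in 6.4.3.1*. This keeps both promised variants.

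Add a sentence stating that a subject whose symptoms are unresolved when she starts Cycle 2 or non-study antifungal therapy stays in the Cycle 1 risk set as not resolved to the end of planned Cycle 1 follow-up. State that the median, its confidence interval and the log-rank test are computed on that basis.

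The cost is SAP wording and a small programming change, with no new data. The resolution figures may be slightly less favourable.

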10.1.1. Study Visits

The study will consist of a Screening visit on Day -2 (± 1), Baseline visit on Day 1 (if applicable, the Screening and Baseline visits can both be done on Day 1), Phone contacts on Days 3, 5 and 7 (± 1), a TOC visit 14 (± 3) days after Baseline, FU visits at: 14 (± 3) days after EOT, 30 (± 4) after Baseline, 30 (± 4) after EOT and 60 (± 4) days after EOT.

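### The exploratory log-rank test of 3 versus 7 days runs on an assessment schedule that depends on the arm, so for resolutions first seen after TOC identical arms can look different

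*SAP*

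**What the plan says.** SAP 6.4.3.1 defines the endpoint as the "time from initiation of study treatment until resolution of the symptom, which is measured by VSS score = 0". On follow-up it adds: "The data will be collected from initiation of study treatment to last FU visit in Cycle 1 and Cycle 2 separately". SAP 6.4.3.2 then specifies Kaplan-Meier curves, Brookmeyer-Crowley medians and, within Group B, a log-rank test: "Pairwise treatment comparisons of subjects in group B 3 days vs. subjects in group B 7 days will be performed using log-rank test".

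No diary or recalled resolution date is described. Protocol 14.8 has subjects rate symptoms after baseline "during telephone interviews on Days 3, 5 and 7, at the TOC visit and at the FU visits", and at unscheduled visits as needed. Signs are not rated by phone: Protocol 14.11 has the investigator rate "signs of infection at the Screening, TOC and first FU visits at 14 days after EOT", and at later follow-up visits only if symptoms are present.

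Protocol 10.1.1 places "a TOC visit 14 (± 3) days after Baseline" and the follow-up visits at "14 (± 3) days after EOT, 30 (± 4) after Baseline, 30 (± 4) after EOT and 60 (± 4) days after EOT". Protocol section 15 acknowledges that visits depend on the dosing group and may overlap. The SAP gives no event-time rule, no interval-censored method, no rule for overlapping visits, and no censoring rule for subjects who enter Cycle 2.

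**The concern.** The log-rank test compares, at each event date, the resolutions in one arm with those expected from everyone still at risk. That is a fair comparison only if both arms are looked at on the same days. Here the treatment being compared moves three of the visits. When one arm has a visit and the other does not, only the first can record an event, although the second may have just as many unrecorded resolutions.

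At stake is one exploratory p-value on treatment duration, the only randomised contrast in the study. SAP 6.1 reads all tests at a two-sided 5% level, and this test's error rate need not be 5%.

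**Working it through.** The plan states no effect size, event count or power for this test, so it offers no figure to reproduce.

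**Visit days.** Baseline is Day 1. EOT is Day 3 or Day 7 (Protocol synopsis, Baseline visit), that is Baseline+2 or Baseline+6.

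| Contact | 3-day arm | 7-day arm |
|---|---|---|
| Phone Days 3, 5, 7 | +2, +4, +6 | +2, +4, +6 |
| TOC (V3) | +14 | +14 |
| V4, EOT+14 | +16 | +20 |
| V5 | +30 | +30 |
| V6, EOT+30 | +32 | +36 |
| V7, EOT+60 | +62 | +66 |

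**Worked case.** Assumptions: 50 per arm (SAP 5.4), identical exponential times, 50.5% resolved by Day 14 (composite cure in the first earlier trial, Protocol 7.1.4, used only as a reference), visits on their nominal days, and unresolved subjects censored at their last visit. Then λ = −ln(0.495)/14 = 0.0502 and S(t) = exp(−λt). The expected number at risk is 50 × S(previous visit in that arm). Expected events are 50 × [S(previous visit) − S(this visit)]. O−E for the 3-day arm is d₃ − (d₃+d₇)·n₃/(n₃+n₇). Up to TOC it is zero.

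| Day | At risk 3 / 7 | Events 3 / 7 | O−E, 3-day |
|---|---|---|---|
| +16 | 24.75 / 24.75 | 2.37 / 0 | +1.18 |
| +20 | 22.38 / 24.75 | 0 / 6.44 | −3.06 |
| +30 | 22.38 / 18.31 | 11.30 / 7.23 | +1.11 |
| +32 | 11.08 / 11.08 | 1.06 / 0 | +0.53 |
| +36 | 10.02 / 11.08 | 0 / 2.88 | −1.37 |
| +62 | 10.02 / 8.20 | 7.80 / 0 | +3.51 |
| +66 | 0 / 8.20 | 0 / 6.38 | 0 |

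The sum is +1.90. The hypergeometric variance is 10.10 up to TOC plus 6.63 after it, 16.73 in all. So Z ≈ 1.90/√16.73 = 0.46, and the apparent hazard ratio (3 vs 7 days) is exp(1.90/16.73) = 1.12. With Z centred at 0.46, rejection is Φ(−1.50) + Φ(−2.42) = 0.067 + 0.008 ≈ 7.5%.

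The early rows largely cancel. Most of the net shift comes from the last visit: at +62 the 3-day events are set against 7-day subjects still at risk, but by +66 no 3-day subject is left for the reverse comparison.

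**Simulation.** Identical arms, 50 per arm, exponential times, visit windows applied, 3,000 runs per case. Entries are the rejection rate of the 5% test and, except in the last column, the apparent hazard ratio. In the Cycle 2 columns, half of those unresolved leave at TOC and again at EOT+14 and are censored.

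| Resolved by Day 14 | As planned, phone ratings | As planned, no phone ratings | Cycle 2 exits, phone | Cycle 2 exits, no phone | Common contacts only, phone / no phone |
|---|---|---|---|---|---|
| 40% | 10.8%, 1.18 | 11.9%, 1.20 | 5.1%, 1.08 | 7.3%, 1.11 | 5.5% / 5.1% |
| 50.5% | 7.4%, 1.12 | 8.4%, 1.12 | 5.5%, 1.04 | 7.2%, 1.09 | 5.1% / 6.1% |
| 63.3% | 5.7%, 1.04 | 6.0%, 1.07 | 5.2%, 1.03 | 6.9%, 1.10 | 5.0% / 5.2% |
| 80% | 5.7%, 1.00 | 6.3%, 1.07 | 5.8%, 1.03 | 8.3%, 1.14 | 4.8% / 5.9% |

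The no-phone columns apply if signs must also clear. SAP 6.4.3.1 speaks of symptoms, while 6.4.3.2 speaks of signs and symptoms.

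Further runs went down to 32% resolved by Day 14, a median of 25 days: 1 − exp(−ln 2 × 14/25) = 0.32. With nobody leaving, that case rejected 18–19%. With the Cycle 2 exits, rejection was 5–11% across medians of 7 to 25 days. An interval-censored score test gave 3–6% and the common-contact log-rank test 4–6% (700 runs per case, simulation error √(0.05 × 0.95/700) ≈ 0.8 points).

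**Direction.** If the overlapping pairs V3/V4 and V5/V6 are each done as one visit in the 3-day arm, the mean Z at a 7-day median moves from +0.10 to −0.49 with phone ratings and from +0.39 to −0.94 without, that is towards 7 days.

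**The case against.** The endpoint is exploratory, SAP 6.1 says the study is not powered for formal comparisons, and the primary endpoint sits at the Baseline-anchored TOC. Five of the eight contacts are common to both arms. The earlier cure rates of 50.5% and 63.3% required signs and symptoms to clear, and symptoms alone clear no later, so the share resolved by TOC could be higher here. Subjects who do badly may leave for Cycle 2, which removes many of the late events that drive the bias.

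All of this is fair and sets the severity. It does not remove the problem. Protocol 7.2.1 says the earlier trials excluded treatment failures and immunocompromised patients, so slower resolution here is plausible, though not documented. The SAP also states no censoring rule for Cycle 2 entry, so that attenuation cannot be counted on.

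A reader might infer four stronger things that the documents do not support:

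- **A false-positive rate near 20% is to be expected.** That needs slow resolution and nobody leaving for Cycle 2.
- **The test always favours 3 days.** It usually does, but merging overlapping visits can reverse the direction.
- **Every event at V4, V6 or V7 is recorded four days late in the 7-day arm.** The later visit also catches more resolutions. At 50.5% resolved by Day 14, the mean recorded day among resolvers was 22.9 in the 3-day arm and 22.5 in the 7-day arm.
- **The Kaplan-Meier medians are shifted by the schedule.** They are affected only if they fall after TOC.

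**Conclusion.** The point holds, as a minor one. The assessment schedule depends on the arm, the planned log-rank test ignores this, and nothing in either document corrects for it. Only resolutions first seen after TOC are affected.

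The size rests on assumptions the documents cannot settle: the share resolved by TOC, the shape of the resolution times (exponential here), whether signs count, and how many subjects leave for Cycle 2. The excess over 5% is small if half or more resolve by Day 14, or if many of those unresolved leave for Cycle 2 and are censored. It is material only if resolution is slow and subjects stay in Cycle 1. The SAP does not say outright that the visit date is the event date, but it describes no other source.

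**What to change.** In SAP 6.4.3.2, do one of two things:

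- Replace the log-rank test on visit dates with an interval-censored log-rank (score) test, using the interval from the last contact with symptoms to the first without.
- Keep the log-rank test but count events only at the Baseline-anchored contacts common to both arms: Days 3, 5 and 7, TOC and V5.

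In the same edit, state the event-time rule and the censoring rule at Cycle 2 entry, and say whether the event is resolution of symptoms or of signs and symptoms.

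The cost is SAP text and slightly more analysis work. The second option leaves the late EOT-anchored assessments out of this one test. No visit, procedure or collected data changes.
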